### 5.1.3 Study treatment completion/discontinuation

A subject is considered to have prematurely discontinued treatment in the RI period if on the **Study Treatment Log** the 'Study period' is 'Single-Blind Run-in' and 'Reason for treatment stop' is 'Discontinued'.

A subject is considered to have prematurely discontinued study treatment in the DB (SB aprocitentan, DB-WD, respectively) part if on the **Study Treatment Log** the 'Reason for treatment stop' is 'Discontinued' for the corresponding 'Study period'.

Reasons for premature discontinuation are collected on the same form and include: AE, lack of efficacy, withdrawal by subject, lost to FU, death, pregnancy, and other. If the

reason for premature study treatment discontinuation was related to the COVID-19 pandemic, this was collected.

The numbers of subjects treated in the DB, SB aprocitentan and DB-WD parts will be tabulated by treatment group in the SAF, rSAF and mSAF, respectively.

The number (%) of subjects with and the reasons for premature treatment discontinuation in the RI period will be summarized based on the RIS.

The number (%) of subjects with and the reasons for premature treatment discontinuation in the randomized treatment period will be summarized by study part and treatment group (within study part) in the SAF, rSAF or mSAF, where appropriate. Reasons for premature study treatment discontinuation related to COVID-19 pandemic will also be summarized.

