## 6.5 Other efficacy endpoints

### 6.5.1 Variables

- Changes from baseline to Week 2 of DB treatment in mean trough SiSBP and SiDBP measured by AOBPM.
- Changes from baseline to Week 4 in daytime and nighttime mean SBP and DBP measured by 24 h ABPM:
  - Daytime is defined as between 09:00 and 21:00.
  - Nighttime is defined as between 01:00 and 06:00 [[O'Brien 2013](#)].
- Changes from DB-WD baseline (Week 36) to Week 38, Week 44 and Week 48 of DB-WD treatment in mean trough SiSBP and SiDBP measured by AOBPM.
- Changes from DB-WD baseline (Week 36) to Week 40 in daytime and nighttime mean SBP and DBP measured by 24 h ABPM.
- Ratios to baseline for all assessed time points in the DB and SB aprocitentan parts and to DB-WD baseline (Week 36) for all assessed time points in the DB-WD part in UACR.
- Discontinuation of randomized study treatment due to lack of efficacy (as collected on the **Study Treatment Log**) by study part (DB, SB aprocitentan and DB-WD).
- Initiation of antihypertensive rescue medication (as indicated on the **Previous/Concomitant Medication** eCRF) in the SB aprocitentan part or DB-WD part. (Rescue medication is not allowed in the DB part).
- Observed values of home SBP/DBP by visit collected due to the COVID-19 pandemic in the DB, SB aprocitentan, and DB-WD parts.

The following endpoints related to BP control and response were added as compared to the protocol [refer to [Section 11](#)]:

- Binary control variables will be created at each visit for SiSBP and SiDBP measured by AOBPM:
  - SBP Control = ‘Yes’ if patient achieved a mean trough SiSBP of < 135 mmHg or < 140 mmHg at the visit. SBP Control= ‘No’ otherwise.
  - DBP Control = ‘Yes’ if patient achieved a mean trough SiDBP of < 85 mmHg or < 90 mmHg at the visit. DBP Control= ‘No’ otherwise.
  - SBP/DBP control = ‘Yes’ if patient achieved a mean trough SiSBP of < 135 mmHg and SiDBP of < 85 mmHg or SiSBP of < 140 and SiDBP of < 90 mmHg at the visit. SBP/DBP control = ‘No’ otherwise.

- Binary response variable will be created at each visit in the DB and SB parts of the study for SiSBP and SiDBP measured by AOBPM:
  - SBP Response = ‘Yes’ if patient achieved a reduction in SiSBP from baseline of  $\geq 10$  mmHg or  $\geq 15$  mmHg in the DB and SB aprocitentan parts. SBP Response = ‘No’ otherwise.

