- *The number (%) of subjects who discontinued study treatment due to lack of efficacy will be tabulated by study part (DB, SB aprocitentan and DB-WD) and treatment group (within study part) in the FAS (2×) and mFAS, respectively. If there are at least 12 subjects discontinued due to lack of efficacy, time from Randomization to treatment discontinuation due to lack of efficacy in the DB or SB aprocitentan part will be summarized by treatment group using Kaplan-Meier plots in the FAS. For subjects who did not discontinue treatment or discontinued treatment for reasons other than lack of efficacy, time to discontinuation will be censored at the last dose of DB or SB treatment (whichever comes last). Additionally, a ‘two-step’ Cox model with a factor for treatment will be fitted [see Section 8.2 for details]. Time from Re-randomization to treatment discontinuation due to lack of efficacy in the DB-WD part will be summarized similarly in the mSAF, except that the Cox model is the conventional one. For subjects who did not discontinue treatment or discontinued treatment for reasons other than lack of efficacy in the DB-WD part, time to discontinuation will be censored at the last DB-WD treatment + 30 days (or EOS date, whichever comes first).*
- *The number (%) of subjects who initiated antihypertensive rescue medication will be summarized by study part (SB and DB-WD; rescue medication is not allowed in the DB part) and treatment group (within study part).*
- *Home SBP/DBP collected due to the COVID-19 pandemic will be summarized by visit in DB, SB and DB-WD parts using descriptive statistics.*
- *The number (%) of subjects with SBP/DBP Control will be tabulated for the DB+SB and DB-WD parts at each visit by treatment group in the FAS and mFAS, respectively. Subjects with a missing value at a given visit will be excluded from the analysis at that visit. The Cochran-Mantel-Haenszel (CMH) test will be used to test for a difference in the Control proportions at Week 4 between treatment groups in DB part on the FAS and at Week 40 between treatment groups in DB-WD part (stratified by randomized*

treatment in the DB part) on the mFAS. The treatment effect will be expressed in terms of the aprocitentan to placebo OR and corresponding 95% CI. An OR > 1 will indicate a benefit of aprocitentan as compared to placebo.

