Change from baseline to Week 4 in mean nighttime DBP	ABPM		ANCOVA	aFAS	Week 4	Included
Change from DB-WD baseline (Week 36) to Week 38 in SiSBP	AOBPM		Mixed model (key secondary)	mFAS	Weeks 38,40	Included
Changes from DB-WD baseline (Week 36) to Weeks 44 and 48 in SiSBP	AOBPM		Mixed model	mFAS	Weeks 38,40, 44, 48	Included
Changes from DB-WD baseline (Week 36) to Week 38 in SiDBP	AOBPM		Mixed model	mFAS	Weeks 38,40	Included

Endpoint	Measured by	Analysis	Model	Analysis set	Visits	Data after intercurrent event*
Changes from DB-WD baseline (Week 36) to Weeks 44 and 48 in SiDBP	AOBPM		Mixed model	mFAS	Weeks 38,40, 44, 48	Included
Change from DB-WD baseline (Week 36) to Week 40 in mean daytime SBP	ABPM		ANCOVA	maFAS	Week 40	Included
Change from DB-WD baseline (Week 36) to Week 40 in mean nighttime SBP	ABPM		ANCOVA	maFAS	Week 40	Included
Change from DB-WD baseline (Week 36) to Week 40 in mean daytime DBP	ABPM		ANCOVA	maFAS	Week 40	Included
Change from DB-WD baseline (Week 36) to Week 40 in mean nighttime DBP	ABPM		ANCOVA	maFAS	Week 40	Included
Ratio to baseline of UACR			Mixed model	FAS	Week 2 up to Week 36	Included
Ratio to DB-WD baseline (Week 36) of UACR			Mixed model	mFAS	Week 38 up to Week 48	Included
Time from Randomization to discontinuation of study treatment due to lack of efficacy			Cox model (two-step)	FAS	NA	NA
Time from Re-randomization to discontinuation of study treatment due to lack of efficacy			Cox model	mFAS	NA	NA

\* In the DB part: Premature DB treatment discontinuation or addition / dose increase of diuretic (whichever comes first); in the DB-WD part: Premature DB-WD treatment discontinuation, initiation of antihypertensive rescue medication or addition / dose increase of diuretic (whichever comes first).

ABPM = ambulatory blood pressure monitoring; aFAS = ABPM Full analysis set; ANCOVA = analysis of covariance; AOBPM = automated office blood pressure measurement; CR = Copy Reference; DB = double-blind; DBP = diastolic blood pressure; FAS = Full analysis set; J2R = Jump to Reference; LOCF = last observation carried forward; maFAS = modified ABPM Full analysis set; mFAS = modified Full analysis set; mPPS = modified Per-Protocol set; NA = not applicable; PPS = Per-Protocol Set; SiDBP = (mean trough) sitting diastolic blood pressure; SiSBP = (mean trough) sitting systolic blood pressure; UACR = urine albumin-to-creatinine ratio; WD = withdrawal.

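### In the DB-WD part, time to stopping treatment for lack of efficacy is censored up to 30 days after the last dose, when the event can no longer occur; text and Table 4 also name different analysis sets

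*SAP*

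**What the plan says.** **Event.** SAP section 6.5.1 defines the endpoint as "Discontinuation of randomized study treatment due to lack of efficacy (as collected on the" Study Treatment Log. Section 5.1.3 shows that lack of efficacy is one of several reasons recorded for a treatment stop: "Reasons for premature discontinuation are collected on the same form and include: AE, lack of efficacy, withdrawal by subject" and others.

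**Censoring in DB and SB.** For subjects without the event, section 6.5.2 states that "time to discontinuation will be censored at the last dose of DB or SB treatment (whichever comes last").

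**Censoring in DB-WD.** Later in the same bullet the rule becomes "time to discontinuation will be censored at the last DB-WD treatment + 30 days", or at the EOS date if that is earlier. It covers subjects who did not discontinue and those who "discontinued treatment for reasons other than lack of efficacy in the DB-WD part".

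**Analysis set.** The section 6.5.2 text says that the DB-WD time-to-event analysis "in the DB-WD part will be summarized similarly in the mSAF". The Table 4 row "Time from Re-randomization to discontinuation of study treatment due to lack of efficacy" lists the mFAS.

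**The concern.** A subject who has taken the last dose cannot stop treatment again. Someone who stops for an adverse event on day 20 would still count as at risk of stopping for lack of efficacy until as late as day 50. Events are timed at the stop, while censoring is moved up to 30 days later, so the denominators at later event times include people who cannot contribute an event. At stake are the Kaplan-Meier curve and the conventional Cox model for this endpoint in DB-WD.

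The analysis-set conflict is a separate matter. The mFAS (section 4.1.5) groups subjects by assigned treatment and needs a DB-WD baseline SiSBP. The mSAF (section 4.1.12) groups them by treatment received and needs at least one DB-WD dose. A programmer cannot follow both the text and the table.

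**Working it through.** The plan states no event rate, sample size or power for this endpoint, so there is no figure to reproduce. The check compares the SAP's own rules and then sizes the effect under assumed rates.

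**1. The rules side by side**

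| SAP section | Outcome | Censoring of subjects without the event |
|---|---|---|
| 6.5.2 | Stop for lack of efficacy, DB/SB | Last dose |
| 5.5.1 | Any premature stop, DB/SB | Last dose |
| 5.5.1 | Any premature stop, DB-WD | Handled in the same way as DB/SB |
| 6.5.2 | Stop for lack of efficacy, DB-WD | Last dose + 30 days, or EOS |
| 7.1.2 | Oedema/fluid retention, DB-WD | Last dose + 30 days, or EOS |
| 7.6.1 | MACE-plus, DB-WD | Last dose + 30 days, or EOS |

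For the two safety outcomes the extension fits, because section 7.1.1.1 counts DB-WD events as treatment-emergent up to 30 days after end of treatment. The SAP gives no reason for applying it to a treatment stop.

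**2. Formula for the effect of early stoppers**

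Let λ and μ be constant daily hazards of stopping for lack of efficacy and for other reasons. From day 30 on, the risk set under the +30-day rule holds those still on treatment plus those who stopped for other reasons in the previous 30 days. The apparent hazard is then λ multiplied by

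1 / [1 + (μ/(λ+μ)) × (e^{30(λ+μ)} − 1)].

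Before day 30, replace 30 by t.

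**3. Hazard ratio.** Inputs: DB-WD lasts 84 days (section 2.1). Assumed: no true effect, 5% lack-of-efficacy stops in each arm, and other-reason stops of 20% in one arm and 5% in the other.

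- λ = −ln(0.95)/84 = 0.000611.
- 20% arm: μ = −ln(0.80)/84 = 0.002656; λ+μ = 0.003267. Factor = 1/[1 + 0.813 × (e^{0.0980} − 1)] = 1/(1 + 0.813 × 0.1030) = 0.923.
- 5% arm: μ = 0.000611; λ+μ = 0.001221. Factor = 1/[1 + 0.5 × (e^{0.0366} − 1)] = 1/(1 + 0.5 × 0.0373) = 0.982.
- Averaged over days 0 to 84, including the rise over the first 30 days, the factors are 0.936 and 0.985. Their quotient is 0.951, a shift of about 5%.
- With equal other-reason stopping, the factors are almost the same in both arms and cancel.

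**4. Simulation under assumed rates.** 380 subjects randomized 1:1 (the minimum expected in section 2.1), end of treatment at day 84 ± 4, 400 runs per scenario. Runs with fewer than 12 events, or with no event in one arm, were dropped. Figures are medians. The first three columns are aprocitentan vs placebo (the first two are assumed rates, the third the hazard ratio); every arrow runs from the last-dose rule to the +30-day rule.

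| Lack-of-efficacy stops | Other stops | Hazard ratio | KM, aprocitentan | KM, placebo |
|---|---|---|---|---|
| 3% vs 8% | 5% vs 5% | 0.337 → 0.338 | 2.9% → 2.7% | 8.2% → 7.9% |
| 3% vs 8% | 15% vs 15% | 0.343 → 0.346 | 2.9% → 2.7% | 8.2% → 7.6% |
| 5% vs 15% | 10% vs 10% | 0.311 → 0.311 | 5.0% → 4.8% | 15.7% → 14.6% |
| 3% vs 8% | 20% vs 5% | 0.354 → 0.337 | 3.0% → 2.7% | 8.3% → 8.0% |
| 3% vs 8% | 5% vs 20% | 0.376 → 0.399 | 3.23% → 3.18% | 8.2% → 7.6% |
| 5% vs 5% | 20% vs 5% | 0.992 → 0.939 | 5.2% → 4.8% | 5.2% → 4.8% |
| 5% vs 5% | 5% vs 20% | 0.989 → 1.049 | 5.3% → 4.8% | 5.1% → 4.8% |

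The median within-run ratio of hazard ratios is 0.999 to 1.001 in the balanced scenarios and 0.952 to 1.050 in the unbalanced ones, in line with step 3. The Kaplan-Meier differences run from 0.05 points (3.23 − 3.18) to about 1.2 points (15.73 − 14.56).

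**5. What the 1.2 points contain.** For 15% lack-of-efficacy and 10% other stops, the step 2 formula gives an average factor of 0.969. The cumulative hazard at day 84 falls from 0.1625 to 0.1625 × 0.969 = 0.1575, so incidence falls from 15.0% to 14.6%, or 0.4 points. The rest of the simulated gap comes from reading the curve at its last event. Between days 80 and 88 the +30-day rule also keeps subjects who have already completed treatment in the denominator. After that window there are no events and the extra days change nothing.

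**The case against.** **The EOS cap.** Early stoppers cause the shift in the hazard ratio, and some stop through withdrawal, loss to follow-up or death, which section 5.1.2 also lists as reasons for leaving the study. For them EOS can fall well before day 30. This stands: the calculations do not model the cap, so they overstate the effect for such subjects. It does not rescue the rule, because EOS is otherwise planned 30 days after end of treatment (Table 6).

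**"Too low" depends on the target.** The SAP does not state one. With 6% lack-of-efficacy and 10% other stops, the proportion actually observed to stop for lack of efficacy is (0.0619/0.1672) × (1 − 0.94 × 0.90) = 5.7%, below the 6% that the last-dose rule estimates. This also stands. Incidence is low relative to the last-dose rule, not against every possible target. But adding 30 days to each subject's own last dose is not a recognised competing-risks method.

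**Tempting stronger readings.** A reader might note that total time at risk grows by about 35 to 39% and infer distorted event rates, or might infer wrong at-risk tables after Week 12. Section 6.5.2 plans counts, Kaplan-Meier plots and a Cox model here. It specifies neither an exposure-adjusted rate nor an at-risk table for this endpoint; those appear for other outcomes. A reader might also infer a bias between arms. That needs clearly unequal other-reason stopping, and the 20% vs 5% split is an assumption with no basis in the documents.

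**Analysis set.** The mSAF is defensible in principle, since section 5.5.1 uses it for all-cause stopping in DB-WD. The conflict with Table 4 remains.

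**Conclusion.** The point holds as a minor error of specification. The DB-WD rule keeps subjects in the risk set after the event has become impossible, and it departs without explanation from the rule for the same endpoint in DB/SB. Relative to last-dose censoring, Kaplan-Meier incidence is about 0.05 to 1.2 percentage points lower. The hazard ratio is essentially unchanged with balanced other-reason stopping, and moves by about 5% in either direction at 20% vs 5%. These sizes rest on assumed rates (3 to 15% lack-of-efficacy and 5 to 20% other-reason stops), constant hazards and no EOS cap.

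The mSAF/mFAS conflict is real and independent of the censoring question. The mFAS is better supported: section 6.5.2 already tabulates the DB-WD count for this endpoint in the mFAS, and for DB/SB both text and Table 4 use the FAS.

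The endpoint is one of the other efficacy endpoints, tested without multiplicity correction, and its time-to-event summary appears to depend on at least 12 events. Nothing here supports doubt about the primary or key secondary analysis.

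**What to change.** In the lack-of-efficacy bullet of SAP section 6.5.2:

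- Censor DB-WD subjects without the event at their last dose of DB-WD treatment, as in DB/SB.
- Replace mSAF by mFAS for the DB-WD time-to-event analysis, to match Table 4 and the count in the same bullet.

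Keep the 30-day extension for oedema/fluid retention and MACE-plus. The cost is an edit to the closing sentences of one bullet and the matching program line. No new data are needed and no other analysis changes.

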  - DBP Response = ‘Yes’ if patient achieved a reduction in SiDBP from baseline of  $\geq 5$  mmHg or  $\geq 10$  mmHg in the DB and SB aprocitentan parts. DBP Response = ‘No’ otherwise.
  - SBP/DBP Response = ‘Yes’ if patient achieved a reduction in SiSBP from baseline of  $\geq 10$  mmHg and SiDBP of  $\geq 5$  mmHg or achieved a reduction in SiSBP from baseline  $\geq 15$  mmHg and SiDBP of  $\geq 10$  mmHg at the visit. SBP/DBP response = ‘No’ otherwise.
- A binary response variable will also be created for each visit in the DB-WD part (in which a blood pressure increase may occur)
  - SBP Withdrawal Response = ‘Yes’ if patient achieved an increase in SiSBP from DB-WD baseline of  $\geq 5$  mmHg or  $\geq 10$  mmHg in the DB-WD part. SBP Withdrawal Response = ‘No’ otherwise.
  - DBP Withdrawal Response = ‘Yes’ if patient achieved an increase in SiDBP from DB-WD baseline of  $\geq 3$  mmHg or  $\geq 6$  mmHg in the DB-WD part. DBP Withdrawal Response = ‘No’ otherwise.
  - SBP/DBP Withdrawal Response = ‘Yes’ if patient achieved an increase in SiSBP from DB-WD baseline of  $\geq 5$  mmHg and SiDBP of  $\geq 3$  mmHg or an increase in SiSBP from DB-WD baseline of  $\geq 10$  mmHg and SiDBP of  $\geq 6$  mmHg. SBP/DBP Withdrawal response = ‘No’ otherwise.

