- *The number (%) of subjects with SBP/DBP Response* will be tabulated for the DB+SB and DB-WD parts at each visit by treatment group in the FAS and mFAS, respectively. Similar analyses as for control will be done at Week 4 and Week 40.

The analyses of the other endpoints are summarized in [Table 4](#).

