## 8.2 Analysis details

### 8.2.1 Mixed model for repeated measurements

This model is used, for example, for the main analyses of the primary and the key secondary endpoints.

Assuming the data are in ‘long’ format (i.e., one row for each subject/visit) example SAS® statements for the primary endpoint analysis are:

```
proc mixed data=db;
  class subjid trt01pn avisitn;
  model chg=trt01pn avisitn trt01pn*avisitn base base*avisitn/ ddfm=kr;
  repeated avisitn/ subject=subjid type=un;
  lsmeans trt01pn*avisitn/ diff=control ('3' '6') alpha=0.025;
run;
```

The data set *db* includes baseline SiSBP (*base*) as well as changes (*chg*) from baseline to Weeks 2 and 4. Furthermore, *trt01pn* equals 1, 2 and 3 for aprocitentan 12.5 mg, aprocitentan 25 mg and placebo in the DB part, respectively, and *avisitn* is 5 and 6 for Weeks 2 and 4, respectively. The Bonferroni correction [Section 6.1] will be applied by comparing the two-sided p-values vs 0.025 (rather than adding *adjust=bonf* to the *lsmeans* statement).

Again, assuming the data are in ‘long’ format example SAS® statements for the secondary endpoint analysis are:

```
proc mixed data=dbwd;
  class trt01pn subjid trt03pn avisitn;
  model chg=trt01pn trt03pn avisitn trt03pn*avisitn wk36 wk36*avisitn/
  ddfm=kr;
  repeated avisitn/ subject=subjid type=un;
  lsmeans trt03pn*avisitn/ diff=control ('5' '13') alpha =0.05(1);
run;
```

The data set *dbwd* includes DB-WD baseline (Week 36) SiSBP (*wk36*) as well as changes (*chg*) from DB-WD baseline (Week 36) to Weeks 38 and 40. Furthermore, *trt03pn* equals 4 and 5 for aprocitentan 25 mg and placebo in the DB-WD part, respectively, and *avisitn* is 12 and 13 for Weeks 38 and 40, respectively. Note that *trt01pn* (treatment in the DB part) is now used as a stratum.

 The alpha level needs to be adjusted to 0.025 in case one of H10 and H20 has been rejected.

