### 8.2.5 Control/response analysis

This analysis will be implemented by the following SAS® statement:

```
proc freq;  
  tables treatment*response / nocol nopercnt cmh1 commonriskdiff;  
run;
```

For DB-WD the analysis should be stratified by DB treatment, so treatment in DB (trt01pn) needs to be added in the tables statement.

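### Exploratory control/response analyses: the odds-ratio reading is reversed for Week 40 Withdrawal Response, and the Section 8.2.5 code, run on three arms, gives no odds ratio

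*SAP*

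**What the plan says.** SAP Section 6.5.2 compares the proportions with blood-pressure control by a CMH test. This is done at Week 4 in the FAS and at Week 40 in the mFAS, the latter stratified by treatment in the double-blind (DB) part. On the effect measure it says: "The treatment effect will be expressed in terms of the aprocitentan to placebo OR and corresponding 95% CI". The next sentence gives the reading: "An OR > 1 will indicate a benefit of aprocitentan as compared to placebo". The following bullet, on Response, says "Similar analyses as for control will be done at Week 4 and Week 40" and gives no direction of its own.

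Section 6.5.1 defines two kinds of response:

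- The reduction type is confined to the first two parts: "Binary response variable will be created at each visit in the DB and SB parts of the study".
- For the withdrawal (DB-WD) part it defines Withdrawal Response, which is Yes "if patient achieved an increase in SiSBP from DB-WD baseline of" at least 5 or at least 10 mmHg. The diastolic thresholds are 3 and 6 mmHg.

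Section 8.2.5 presents a single statement as the implementation: "tables treatment*response / nocol nopercnt cmh1 commonriskdiff". Its only adaptation note is "For DB-WD the analysis should be stratified by DB treatment". The DB treatment variable is coded in Section 8.2.1, where it "equals 1, 2 and 3 for aprocitentan 12.5 mg, aprocitentan 25 mg and placebo in the DB part". Table 4, the summary of efficacy analyses, has no row for Control or Response. Section 11 calls these endpoints exploratory, and Section 6.5.2 tests them at a two-sided 0.05 without multiplicity correction.

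**The concern.** There are two separate problems.

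**Direction.** The reading suits Control, and it suits Response at Week 4, because Yes is favourable in both. At Week 40 it is carried to an endpoint where Yes is unfavourable. A reader who applies the stated rule would take a protective effect for harm, against the percentages tabulated beside it.

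**Code.** The text promises an odds ratio of aprocitentan to placebo. The statement in Section 8.2.5 does not separate the two doses, requests a common risk difference that Section 6.5.2 does not name, and fixes no order for the response levels. Run on the three DB arms, it does not give the promised estimate, and its p-value can miss an effect of 25 mg.

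**Working it through.** The documents give no rates, power or sample size for these endpoints, so there is no planned figure to reproduce. All rates below are assumptions.

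**1. Direction at Week 40**

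The odds ratio is [pA/(1−pA)] / [pP/(1−pP)], where A is aprocitentan and P is placebo.

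- Withdrawal Response, 30% vs 50%. For Yes: (0.30/0.70)/(0.50/0.50) = 0.43. For No: (0.70/0.30)/(0.50/0.50) = 2.33.
- Control, 50% vs 30%. For Yes: (0.50/0.50)/(0.30/0.70) = 2.33. For No: 0.43.

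So if both endpoints use one level order, the rule misreads exactly one of them: Withdrawal Response with Yes first, Control with No first.

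The result does not hinge on these rates. I took a normal model for the change, with a mean placebo rise of 0 to 6 mmHg, a benefit of 2 to 8 mmHg and an SD of 10 to 20 mmHg. The odds ratio for Yes is then 0.24 to 0.85 at the 5 mmHg threshold and 0.20 to 0.85 at 10 mmHg, always below 1.

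**2. The Section 8.2.5 statement at Week 4**

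Inputs: three arms allocated 1:1:1 and 730 randomised (Section 2.1), so about 730/3 ≈ 243 per arm and N = 729. Row scores are 1, 2, 3 for 12.5 mg, 25 mg and placebo (Section 8.2.1; Section 8.1 lists the arms in the same order). That the CMH1 option requests the 1-df correlation statistic is general knowledge of the software, not something the SAP states. A 3×2 table has no single odds ratio.

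The correlation statistic is Q = (N−1)r². With equal arms and equally spaced scores it reduces to

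Q = (N−1)(p12.5 − pPlacebo)² / [6 p̄(1−p̄)],

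where p̄ is the mean of the three rates. The 25 mg rate enters only through p̄, so the test is in effect 12.5 mg against placebo.

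For one dose against placebo (486 subjects), Q = 485 d² / [4 p̄(1−p̄)], where d is the difference in rates and p̄ the mean of the two rates.

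Example, 40/50/30%:

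- Three-arm: 728 × 0.10² / (6 × 0.40 × 0.60) = 5.06, p = 0.025.
- 25 mg vs placebo: 485 × 0.20² / (4 × 0.40 × 0.60) = 20.21, p = 0.000007.

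Power is from 20,000 simulated trials at two-sided 0.05.

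| Assumed rates, 12.5 mg / 25 mg / placebo | Three-arm Q (p) | 25 mg vs placebo: OR, Q (p) | Power, three-arm vs pairwise |
|---|---|---|---|
| 45/45/30% | 11.38 (0.0007) | 1.91, 11.64 (0.0006) | 92% vs 93% |
| 40/50/30% | 5.06 (0.025) | 2.33, 20.21 (0.000007) | 61% vs 99% |
| 35/45/30% | 1.31 (0.25) | 1.91, 11.64 (0.0006) | 20% vs 93% |
| 30/50/30% | 0 (1.0) | 2.33, 20.21 (0.000007) | 4% vs 99% |

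Week 40 has two arms, so each stratum is a 2×2 table. The 1-df statistic is then the usual CMH test and a common odds ratio exists.

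**The case against.** The best defence on direction is that the sentence sits in the Control bullet, where it is correct. The Response bullet does not repeat it, and a similar analysis need not mean an identical reading. The level order could also be set separately for each endpoint, which would make the rule true for both. This stands only in part. If the reading does not carry over, Withdrawal Response has no stated direction at all. If it is to be rescued by reversing the levels for one endpoint, the plan has to say so. Either way the same sentence is missing.

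On the code, Section 1 says that code illustrates the analyses, the statement is plainly a template, and a promised odds ratio against placebo implies two-group tables. A programmer who ran three arms would also notice that no odds ratio was printed. These are fair points, and they make this part conditional on a literal run. Against them, Section 8.2.5 presents the statement as the implementation, and its one adaptation note concerns the withdrawal part only.

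It is also true that the losses rest on assumed rates, that almost nothing is lost when the two doses perform alike, and that the endpoints are exploratory.

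**Conclusion.** The concern holds on both counts. The odds-ratio reading, carried over as written, is reversed for Week 40 Withdrawal Response when the ratio refers to Yes. This follows from the SAP's definitions and needs no assumed rate. The code problem applies if the statement is run on all three DB arms. The promised odds ratio is then not produced, and the loss for 25 mg ranges from almost none (equal dose effects) to complete (12.5 mg no better than placebo), given about 243 per arm and the assumed rates. The stratified two-arm Week 40 test is sound. H10, H20 and H30 are not affected. The change should be made, but the importance is moderate because the endpoints are exploratory.

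**What to change.** - In Section 6.5.2, state that for Withdrawal Response an odds ratio below 1 favours aprocitentan. Alternatively, analyse absence of the increase, so that a value above 1 is a benefit throughout.
- In Section 8.2.5, replace the Week 4 statement by two 2×2 CMH analyses: 12.5 mg vs placebo and 25 mg vs placebo.
- Fix the row and column order so that the odds ratio refers to the stated event for aprocitentan relative to placebo.
- Output the odds ratio (the common odds ratio at Week 40) with its 95% CI, in place of or alongside the common risk difference.
- Keep the Week 40 stratification by DB treatment.

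The cost is one sentence of text and a few lines of code. No new data are needed, and the confirmatory tests do not change.
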